1 PROTOCOL SYNOPSIS

Trial Sponsor	Alcon Research, LLC [name]
Name of Test Product(s)	LID018869
Name of Control Product(s)	Control Product 1 (Part A): ACUVUE OASYS® with HYDRACLEAR® PLUS (AOHP) Control Product 2 (Part B): CooperVision® Biofinity® (Biofinity)
Title of Trial	Clinical Comparison of Two Daily Wear Frequent Replacement Silicone Hydrogel Soft Contact Lenses
Protocol Number	CLY935-C020
Number of Sites	~4
Country	US
Planned Duration of Exposure – Part A	~60 days total duration (test and control): Test Product: ~30 days Control Product 1: ~ 30 days (2x ~15 days)
Planned Duration of Exposure – Part B	~30 days total duration (control only) Control Product 2: ~ 30 days
Number of Subjects – Part A	Target to complete: 60 (~30 per each parallel group)
	Planned to enroll: ~66
Number of Subjects – Part B	Target to complete: 60 (~ 30 per each parallel group)
	Planned to enroll: ~66
Study Population	Volunteer subjects aged 18 or over who are habitual spherical [REDACTED] soft contact lens wearers, have at least 3 months of contact lens wearing experience, and who wear their habitual lenses at least 5 days per week and at least 10 hours per day. [REDACTED] [REDACTED] [REDACTED] [REDACTED] [REDACTED] [REDACTED] [REDACTED]

	
[REDACTED]

Objective(s)	
The primary objective of this study is to evaluate the overall performance of an investigational silicone hydrogel lens when compared to AOHP.
 
[REDACTED]
 
[REDACTED]
 
[REDACTED]

Endpoints	
Primary Effectiveness
 
Distance VA (logMAR) with study lenses 
[REDACTED]
 
[REDACTED][REDACTED][REDACTED][REDACTED][REDACTED][REDACTED][REDACTED][REDACTED][REDACTED][REDACTED][REDACTED][REDACTED][REDACTED][REDACTED] 
Safety
 
AEsBiomicroscopy findingsDevice deficiencies
Assessments	
Effectiveness
 
Distance VA (logMAR) with study lensesDistance VA (Snellen) habitual correctionManifest refractionBCVA (Snellen distance with manifest refraction) 
[REDACTED]
 
[REDACTED]
 
[REDACTED]
 
[REDACTED]

	
 • [REDACTED] ■ [REDACTED] 
Safety
 
 • AEs • Biomicroscopy • Device deficiencies 	
Study Design – Part A	 Prospective  Single group  Parallel group  Crossover  Other	 Single-masked (trial subject)  Single-masked (Investigator)  Double-masked  Open-label  Other
	 Contralateral  Bilateral  Monocular lens wear	 Randomized
	Randomization scheme [REDACTED] Sequence 1: LID018869 → AOHP Sequence 2: AOHP → LID018869	
Study Design – Part B	 Prospective  Single group [REDACTED]  Crossover  Other	 Single-masked (trial subject)  Single-masked (Investigator)  Double-masked  Open-label  Other
	 Contralateral  Bilateral  Monocular lens wear	 Randomized

	
contraindicates contact lens wear, as determined by the Investigator.
 
2. Any use of systemic or ocular medications for which contact lens wear could be contraindicated, as determined by the Investigator.
 
3. History of refractive surgery or plan to have refractive surgery during the study or irregular cornea in either eye.
 
■ [REDACTED]
 
■ [REDACTED]
 
■ [REDACTED]
 
6. Current or history of pathologically dry eye in either eye that, in the opinion of the Investigator, would preclude contact lens wear.
 
■ [REDACTED]
 
■ [REDACTED]
 
■ [REDACTED]
 
■ [REDACTED]
 
10. Wearing habitual contact lenses in an extended wear modality (routinely sleeping in lenses for at least 1 night per week) over the last 3 months prior to enrollment.
 
[REDACTED]
 
15. Current habitual wearers of AOHP.^e

--	---

	
[REDACTED]
 
[REDACTED]
 
[REDACTED]
 
[REDACTED]
 
[REDACTED]
 
17. Current habitual wearer of Biofinity family of contact lenses (comfilcon A).
 
■ [REDACTED]
 
[REDACTED]

Associated Materials	
• CLEAR CARE® contact lens solution 
■ [REDACTED]
 
[REDACTED]
 
[REDACTED]
 
[REDACTED]
 
[REDACTED]

Table 1-1 Schedule of Study Procedures and Assessments – Part A

Procedure/ Assessment	PRESCREENING	LENS 1				LENS 2		USV
		Visit 1 Screen/ Baseline/ Dispense Lens 1	Visit 2 Day 15 Follow- up Lens 1	Visit 3 Day 30 Follow-up Lens 1 Dispense Lens 2		Visit 4 Day 15 Follow- up Lens 2	Visit 5 Day 30 Follow- up Lens 2 /Exit^	
				Follow-up Lens 1	Dispense Lens 2			
Informed Consent		X						
Demographics		X						
Medical History*		X	X	X	X	X	X	X
Concomitant Medications*		X	X	X	X	X	X	X
Inclusion/ Exclusion		X						
Habitual (lens brand, lens power*, lens care)		X						
VA w/ habitual correction* (OD, OS, Snellen distance)		X					X	(X)
Manifest Refraction and BCVA with manifest refraction* (OD, OS, Snellen distance)		X	(X)	(X)	(X)	(X)	(X)	(X)
Biomicroscopy		X	X	X		X	X	X
Randomization and record lens power*		X						
Dispense study lenses		X	(X) ^Ω		X	(X) ^Ω		(X)
VA w/ study lenses (OD, OS, logMAR distance)		X	X	X	X	X	X	(X)

Procedure/ Assessment	PRESCREENING	LENS 1			LENS 2			USV
		Visit 1 Screen/ Baseline/ Dispense Lens 1	Visit 2 Day 15 Follow- up Lens 1	Visit 3 Day 30 Follow-up Lens 1 Dispense Lens 2		Visit 4 Day 15 Follow- up Lens 2	Visit 5 Day 30 Follow- up Lens 2 /Exit^	
				Follow-up Lens 1	Dispense Lens 2			
[REDACTED]		■	■	■	■	■	■	■
[REDACTED]		■ ■	■ ■ ■	■ ■ ■	■ ■ ■	■ ■ ■	■ ■ ■	■
[REDACTED]			■	■		■	■	■
[REDACTED]		■ ■	■ ■ ■	■ ■ ■	■ ■ ■	■ ■ ■	■ ■ ■	■
[REDACTED]							■	■
[REDACTED]		■	■	■	■	■	■	■
[REDACTED]		■	■	■	■	■	■	■
AEs [§]		X	X	X	X	X	X	X
Device deficiencies		X	X	X	X	X	X	X
Exit Form		(X)	(X)	(X)	(X)	(X)	X	(X)

USV = Unscheduled visit

[REDACTED]

[REDACTED]

[REDACTED]

[REDACTED]

[REDACTED]

[REDACTED]

[REDACTED]

Table 1-2 Schedule of Study Procedures and Assessments – Part B

Procedure/ Assessment	PRESCREENING	Visit 1 Screen/ Baseline/ Dispense Lens 1	Visit 2	Visit 3 Day 30 Follow-up Lens 1/Exit^	USV
			Day 15 Follow- up Lens 1		
Informed Consent		X			
Demographics		X			
Medical History*		X	X	X	X
Concomitant Medications*		X	X	X	X
Inclusion/ Exclusion		X			
[REDACTED]		■			
Habitual (lens brand, lens power*, lens care)		X			
VA w/ habitual correction* (OD, OS, Snellen distance)		X		X	(X)
Manifest Refraction and BCVA with manifest refraction* (OD, OS, Snellen distance)		X	(X)	(X)	(X)
Biomicroscopy		X	X	X	X
[REDACTED]	■	■			
[REDACTED]		■	■	■	■
Record lens power*		X			
Dispense study lenses		X	(X)		(X)
VA w/ study lenses (OD, OS, logMAR distance)		X	X	X	(X)
[REDACTED]		■	■	■	■
[REDACTED]		■	■	■	■
[REDACTED]		■	■	■	■
[REDACTED]		■	■	■	■
[REDACTED]		■	■	■	■
[REDACTED]		■	■	■	■
[REDACTED]		■	■	■	■
[REDACTED]		■	■	■	■
Collect worn lenses*		(X)	(X)	X	(X)
AEs§		X	X	X	X
Device deficiencies		X	X	X	X

3 INTRODUCTION

3.1 Study Rationale and Purpose

The new contact lens in development is intended for the optical correction of refractive ametropia in persons with non-diseased eyes. The purpose of this study is to evaluate performance of two commercially available daily wear frequent replacement silicone hydrogel soft contact lenses as compared to investigational test product (LID018869) to obtain on-eye performance data [REDACTED]

The primary endpoint was selected to address the primary objective of the study. Procedures for measurement of these endpoints were selected based on common practice for these assessments. [REDACTED]

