3.2 Trial Objective

The primary objective of this study is to evaluate the overall performance of an investigational silicone hydrogel lens when compared to AOHP. [REDACTED]

[REDACTED]

[REDACTED]

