3.5 Outline of Study

Part A of this study will be a multi-site, prospective, randomized, double-masked, [REDACTED] crossover study comparing 2 contact lenses. The expected duration of subject participation in this part is approximately 8 weeks, with 5 scheduled visits. [REDACTED].

Part B will start after Part A has completed. Part B of this study will be a multi-site, prospective, single-arm, single-masked, [REDACTED] study with 1 contact lens. The expected duration of subject participation in Part B of the study is approximately 4 weeks, with 3 scheduled visits. [REDACTED].

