4 TREATMENTS ADMINISTERED

In Part A, subjects will [REDACTED] receive treatment (lens) in a crossover sequence: Test product then Control product 1, or Control product 1 then Test product. In Part B, subjects will only receive one pair of Control product 2 lenses.

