6 ANALYSIS PLAN

Part A and Part B will be summarized and presented separately.

Continuous variables will be summarized using the number of observations, mean, standard deviation, median, minimum, and maximum. Categorical variables will be summarized with counts and percentages from each category.

Any deviations to this analysis plan will be updated during the course of the study as part of a protocol amendment or will be detailed in the clinical study report.

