1.3 Randomization

[REDACTED]

Subjects for Part A of the study will be [REDACTED] [REDACTED] randomized in a 1:1 manner to receive treatment (lens) in a crossover sequence. No randomization will be implemented in Part B.

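### Does the purpose statement promise a Biofinity comparison, and the Part B target a group structure, that the design does not hold?

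*Protocol*

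**What the plan says.** On purpose and objective:

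- Protocol 3.1 states the aim as to "evaluate performance of two commercially available daily wear frequent replacement silicone hydrogel soft contact lenses as compared to investigational test product (LID018869"). The sentence goes on to mention on-eye performance data and is then blacked out.
- Protocol 3.2 is narrower: "The primary objective of this study is to evaluate the overall performance of an investigational silicone hydrogel lens when compared to AOHP". The text after it is blacked out. SAP 1.1 repeats this objective.

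On the design of Part B:

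- Protocol 3.5: "Part B of this study will be a multi-site, prospective, single-arm, single-masked, [REDACTED] study with 1 contact lens". The same section places the start of Part B after the completion of Part A.
- Protocol 4: "In Part B, subjects will only receive one pair of Control product 2 lenses".
- SAP 1.3: "No randomization will be implemented in Part B".
- The Protocol synopsis and SAP 1.4 make Part A double-masked and Part B masked to the subject only.

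On size and reporting:

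- The Protocol synopsis and SAP Table 1-1 use the same phrase for both parts: "Target to complete: 60 (~30 per each parallel group"), with about 66 to be enrolled in each.
- Protocol 6: "Part A and Part B will be summarized and presented separately". SAP 4 and SAP 5 say the same.
- Protocol 6.4.1.1 and SAP 4.2 make no inference on the primary endpoint. The SAP Executive Summary has no success criterion. Protocol 6.10 and SAP 7 give no sample size calculation.

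**The concern.** Two things look wrong on a plain reading.

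The first is the comparison. Section 3.1 puts both marketed lenses on the same footing against LID018869, but only AOHP meets it in a randomised crossover. Part B subjects wear Biofinity alone, at a later time, under weaker masking and with one period instead of two. A Biofinity minus LID018869 difference would mix the lens effect with calendar time, assessor knowledge, period structure and perhaps a different mix of subjects. A report written to the letter of 3.1 could show that difference as if it were comparative evidence. Half of the planned enrolment, 66 of 132, is in the part that supplies no LID018869 data.

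The second is the group split. A single group has no parallel groups, so a target per parallel group looks like text carried over from Part A, where about 30 fits each of the two sequences. If there really were two groups, the readable SAP tables do not mention them, and it would be unclear whether a Part B mean rests on 60 subjects or 30.

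**Working it through.** **Arithmetic of the stated figures.** There is no power calculation to reproduce, since the documents give no alpha, power, effect size, standard deviation or margin. The counts can be checked:

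- Groups: 2 × 30 = 60, which agrees with the target.
- Loss implied by enrolment: 1 − 60/66 = 9.1%. No dropout rate is stated. Planning for 10% gives 60/(1 − 0.10) = 67, or 60 × 1.10 = 66 by the simpler rule. Both fit an approximate 66.
- Sites (Protocol 3.4): 4 × 16 = 64 to 4 × 18 = 72, which brackets 66.
- Share of enrolment in Part B: 66/(66 + 66) = 50%.

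No figure is wrong.

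**What the group split could affect.** The half-width of a 95% interval for one mean, in SD units, is 1.96/√n:

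- n = 60: 1.96/√60 = 0.25
- n = 30: 1.96/√30 = 0.36
- ratio: √(60/30) = 1.41

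The ratio does not depend on the SD. As an illustration only, an assumed SD of 0.10 logMAR gives 0.025 and 0.036. An SD of 0.05 gives 0.013 and 0.018, and an SD of 0.15 gives 0.038 and 0.054. No SD stands in the documents. The primary analysis is limited to descriptive statistics (n, mean, SD, median, minimum and maximum), and no interval appears in the readable plan. The n actually observed will be printed beside each mean, so the planning split cannot misstate it.

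**What a cross-part contrast would look like.** In SD units, 60 Biofinity against 60 LID018869 completers, treated as independent, has half-width 1.96 × √(2/60) = 0.36. The Part A crossover has 1.96 × √(2(1 − ρ)/60), which is 0.30 at an assumed within-subject correlation of 0.3 and 0.11 at 0.9. The cross-part reading is less precise and also open to bias that no interval covers. That would matter if the plan used it. The readable plan contains no such analysis.

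**The group wording, side by side.**

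| Place | Part A | Part B |
|---|---|---|
| Synopsis design boxes, in order | Prospective, Single group (not ticked), Parallel group (ticked), Crossover (ticked), Other | Prospective, Single group (ticked), blacked-out text, Crossover (not ticked), Other |
| SAP Table 1-1 | parallel group, crossover | single group, blacked-out text, single-masked |
| Protocol 3.5 | blacked-out text before the word crossover | blacked-out text after single-masked |

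The blacked-out text in the Part B boxes sits where the parallel-group entry stands for Part A. The sponsor also ticks parallel group and crossover together in Part A, so its use of the term is not exclusive. Part B could be one treatment arm recruited in two subject strata of about 30, which fits both single-arm and the split. It could equally be a carry-over. The readable text cannot settle which.

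**The case for a change.** The case for a change is a fair one. The limits of the Biofinity comparison do not depend on anything blacked out: hidden text cannot make Part B randomised or concurrent with Part A. Calling the study descriptive removes the question of error rates but not of bias, since a descriptive difference across parts carries the same confounding. Section 3.1 does not label the comparison as indirect. Carry-over from Part A is also plausible, because other Part A wording reaches Part B unadapted: SAP 3 promises a listing of lens sequence assignment for both parts, and Protocol 5.3 sends unscheduled visits to Visit 5 and Table 1-1, though Part B ends at Visit 3. The remedy would be wording alone.

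What stands is that 3.1 is wider than the design supports directly, and that a reader should take any Biofinity against LID018869 statement as indirect, non-randomised and non-concurrent. What does not stand is the step to a required change. Section 3.1 claims no randomised or inferential contrast, and its own sentence is partly hidden, as are the other objectives and most of the non-primary analyses. A rule in the SAP forbidding any cross-part difference, or a target rewritten as one group of 60, could contradict text that exists but cannot be read. The absence of groups from the readable SAP tables also proves little: the subgroup section appears in the Protocol contents list, but its text is not readable.

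**Conclusion.** No change to the plan follows. The purpose sentence is a loose statement that the rest of the plan already narrows: one primary objective against AOHP, separate reporting of the two parts, a Part B labelled control-only and unrandomised, no hypothesis and no success criterion. An analyst who follows the SAP will produce a randomised within-subject description of LID018869 and AOHP, and a stand-alone description of Biofinity. Both are sound for what they are.

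The split into groups of about 30 is either a description of recruited strata or a clerical carry-over. The target of 60 and the enrolment of about 66 hold in both cases, and no readable calculation or analysis uses the 30. The 1.41 ratio in precision is therefore a property of a choice that the plan never makes.

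This rests on two assumptions: that the blacked-out sections hold no cross-part analysis presented as a direct comparison, and that the report keeps the parts separate as planned. If the full text does not define the Part B groups, the split is a slip that can be tidied at any convenient revision. Labelling the Biofinity reading in 3.1 as indirect would be equally harmless. Neither would alter a sample size, an analysis or an error rate.

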3.2 Trial Objective

The primary objective of this study is to evaluate the overall performance of an investigational silicone hydrogel lens when compared to AOHP. [REDACTED]

[REDACTED]

[REDACTED]

3.3 Risks and Benefits

Contact lenses may offer improved peripheral vision and the convenience of not wearing spectacles. Material properties and design characteristics of the contact lens in development are features consistent with successful contact lens wear.

[REDACTED]

[REDACTED]

[REDACTED]

[REDACTED]

AOHP contact lenses are commercially available for daily wear use under a biweekly replacement schedule; Biofinity contact lenses are commercially available for daily wear use under a monthly replacement schedule; further details on any known potential risks and benefits can be found in the package insert. Refer to Appendix 13.1 and Appendix 13.2.

The site personnel will educate subjects on proper hygiene and lens handling, and compliance with the use of contact lenses according to the protocol. Subjects should be instructed not to wear contact lenses while sleeping or swimming. The site personnel will also advise the subjects to remove contact lenses and return for prompt follow-up of symptoms, such as ocular discomfort, foreign body sensation, excessive tearing, vision changes, or hyperemia.

3.4 Subject Population

The study population for Part A and Part B each includes approximately 66 volunteer subjects to be enrolled at approximately 4 sites, with approximately 16-18 subjects enrolled per site. The study population will consist of subjects with normal eyes (other than the need for optical correction for myopia), who are adapted, existing wearers of soft contact lenses in both eyes. [REDACTED]

[REDACTED]

3.5 Outline of Study

Part A of this study will be a multi-site, prospective, randomized, double-masked, [REDACTED] crossover study comparing 2 contact lenses. The expected duration of subject participation in this part is approximately 8 weeks, with 5 scheduled visits. [REDACTED].

Part B will start after Part A has completed. Part B of this study will be a multi-site, prospective, single-arm, single-masked, [REDACTED] study with 1 contact lens. The expected duration of subject participation in Part B of the study is approximately 4 weeks, with 3 scheduled visits. [REDACTED].

4 TREATMENTS ADMINISTERED

In Part A, subjects will [REDACTED] receive treatment (lens) in a crossover sequence: Test product then Control product 1, or Control product 1 then Test product. In Part B, subjects will only receive one pair of Control product 2 lenses.

4.1 Identity of Study Treatments – Part A

DESCRIPTION OF TEST AND CONTROL PRODUCTS		
	Test Product	Control Product 1
LID Number	LID018869	N/A
Lens identified in randomization system as:	LID018869	AOHP
Material	Lehfilcon A	Senofilcon A
Water Content	[REDACTED]	38%
Base Curve (mm)	[REDACTED]	8.4 mm, 8.8 mm
Diameter (mm)	[REDACTED]	14.0 mm
[REDACTED]	[REDACTED]	[REDACTED]
Packaging, Labeling, and Supply	
 Blister foil pack [REDACTED] [REDACTED] [REDACTED] [REDACTED] 	
 Blister foil pack Commercial foil Provided in commercial packaging Lenses should be

4.3 Accountability Procedures

[REDACTED]
Designated study staff will provide the study lenses to the subjects in accordance with their randomization schedule. [REDACTED]

It is the Investigator's responsibility to ensure that:

- All study products are accounted for and not used in any unauthorized manner

- [REDACTED]
- [REDACTED]
- [REDACTED]
[REDACTED]
[REDACTED]
[REDACTED]
[REDACTED]

■ [REDACTED]
[REDACTED]

5 STUDY PROCEDURES AND ASSESSMENTS

5.1 Visits and Examinations – Part A

■ [REDACTED]

■ [REDACTED]
[REDACTED]

9	
Based upon the randomized lens sequence assignment, have the subject insert the appropriate Lens 1 study lenses, being careful to maintain the correct OD and OS lens assignments.
 
[REDACTED]
 
[REDACTED][REDACTED]
10	
Evaluate the study lenses by performing:
 
• VA with study lenses (logMAR OD and OS, at distance) 
[REDACTED]
 
[REDACTED]

■	
[REDACTED]
 
[REDACTED][REDACTED] 
[REDACTED]
 
[REDACTED]

12	
Assess and record any AEs and device deficiencies reported or observed during the study visit.
 
[REDACTED]
 
[REDACTED]

13	
Dispense study lens case and lens care solutions (CLEAR CARE contact lens solution).
 
[REDACTED]
 
[REDACTED][REDACTED] 
[REDACTED]

14	Schedule Visit 2 to take place 15 [REDACTED] days after Visit 1. [REDACTED] 
■ [REDACTED]■ [REDACTED]■ [REDACTED]■ [REDACTED]■ [REDACTED]■ [REDACTED]■ [REDACTED]
■	[REDACTED] [REDACTED] [REDACTED] [REDACTED]

5.1.3 Visit 2 (Lens 1: Day 15 Follow-up) – [REDACTED]

1	Obtain information on any changes in medical health and/or the use of concomitant medications.
2	Record any device deficiencies or AEs, including those associated with changes in concomitant medication dosing, which are observed or reported since the previous visit. Collect any ADE/AE/Device Deficiency lenses [REDACTED]
■	[REDACTED]
■	[REDACTED]
5	Evaluate the study lenses by performing: VA with study lenses (logMAR OD and OS, at distance)
6	[REDACTED] 
■ [REDACTED]■ [REDACTED] [REDACTED] [REDACTED]

■	[REDACTED]
■	[REDACTED]
9	Perform slit-lamp biomicroscopy
10	If warranted, perform Manifest Refraction and BCVA with manifest refraction (OD, OS, Snellen distance)
11	Assess and record any AEs and device deficiencies reported or observed during the study visit. [REDACTED]
■	[REDACTED]
13	Schedule Visit 3 to take place 15 [REDACTED] days after Visit 2. [REDACTED]
■	[REDACTED]

5.1.4 Visit 3 (Lens 1: Day 30 Follow-up; Lens 2: Dispense) – [REDACTED]

[REDACTED]

1	Obtain information on any changes in medical health and/or the use of concomitant medications.
---	--

11	Evaluate the study lenses (Lens 2) by performing: 
• VA with study lenses (logMAR OD and OS, at distance) 
[REDACTED]

■	
[REDACTED]
 
■ [REDACTED]■ [REDACTED] 
[REDACTED]

13	Assess and record any AEs and device deficiencies reported or observed during the study visit. 
[REDACTED]

14	Dispense study lens case and lens care solutions (CLEAR CARE contact lens solution) 
[REDACTED]
 
■ [REDACTED] 
[REDACTED]

15	Schedule Visit 4 to take place 15 [REDACTED] days after Visit 3. 
[REDACTED]
 
■ [REDACTED]■ [REDACTED]■ [REDACTED]■ [REDACTED]■ [REDACTED]■ [REDACTED]
■	
[REDACTED]
 
[REDACTED]
 
[REDACTED]
 
[REDACTED]

5.1.5 Visit 4 (Lens 2: Day 15 Follow-up) – [REDACTED]

1	Obtain information on any changes in medical health and/or the use of concomitant medications.
2	Record any device deficiencies or AEs including those associated with changes in concomitant medication dosing, which are observed or reported since the previous visit(s). Collect any ADE/AE/Device Deficiency lenses [REDACTED]
[REDACTED]	[REDACTED]
[REDACTED]	[REDACTED]
5	Evaluate the study lenses by performing: 
• VA with study lenses (logMAR OD and OS, at distance)
[REDACTED]	[REDACTED] 
• [REDACTED]• [REDACTED][REDACTED]
[REDACTED]	[REDACTED] [REDACTED] [REDACTED] [REDACTED]
[REDACTED]	[REDACTED]
9	Perform slit-lamp biomicroscopy
10	If warranted, perform Manifest Refraction and BCVA with manifest refraction (OD, OS, Snellen distance)
11	Assess and record any AEs and device deficiencies reported or observed during the study visit. [REDACTED] [REDACTED]
12	Review and dispense the following with the subject: 
• [REDACTED]

13	Schedule Visit 5 to take place 15 [REDACTED] days after Visit 4. [REDACTED] 
[REDACTED][REDACTED][REDACTED][REDACTED][REDACTED]
[REDACTED]	[REDACTED] [REDACTED] [REDACTED] [REDACTED]

